Purpose and Objectives

The primary objective of this study will be to evaluate the ability for 2 different ureteral access sheaths to obtain and maintain access to the upper collecting system, as well as evaluate ureteral injury using standardized 5-point classification system.

Secondary endpoints will include evaluating ease of instrument passage, stone extraction, device placement, and radiopacity.

Hypothesis

We hypothesize that the modified designs of Re-Trace and Parallel devices will demonstrate similar safety profiles.

Research method

The proposed study is a prospective randomized controlled trial comparing the safety and efficacy of ureteral access sheaths used in flexible ureteroscopy.

Patients scheduled for flexible ureteroscopy will be identified by the investigator at clinic visits or hospital admission at Cleveland Clinic. The research coordinator will approach patients to determine the patient's initial interest in research, and if interested, the consent process will be initiated prior to surgery.

In order to be eligible the patient must be a suitable operative candidate for flexible ureteroscopy and have an abdominopelvic computed tomography (CT) to delineate pre-operative stone size, with measurements captured in greatest axial and coronal dimensions. Patients who have had prior ipsilateral upper urinary tract reconstructive procedures, ureteral stricture, ureteral malignancy, or impacted ureteral stones will be excluded. Pregnant subjects will also be excluded.

Ureteroscopic treatment of renal calculi is a standard of care treatment approach, and participating in this study will not deviate from standard of care ureteroscopy procedures, however, procedures specific to the research will involve being randomized to the use of one of two ureteral access sheaths:

1. Coloplast Re-Trace
2. Cook Flexor Parallel

Choice of sheath length will be left to the discretion of the surgeon based on body habitus and site of pathology, while sheath diameter will be standardized to 12/14F. Smaller diameter sheaths (11/13F, 10/12F) will be used if significant resistance occurs during advancement, otherwise patients will be excluded from the study if unable to gain ureteral access, or if ureteral balloon dilation or semi-rigid ureteroscopy is required to gain ureteral access.

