If unable to obtain access with the initial sheath the patient is randomized to, the patient will be randomized to a backup sheath. If unable to obtain access with backup sheath, then a second backup sheath will be used. If unable to obtain access with any of the three sheaths with diameter 12/14F, an attempt will be made with up to three additional sheaths of a similar smaller diameter (11/13F or 10/12F), in a random order. If access has not been obtained after randomization to 6 sheaths, the patient will be considered a failure and it will be the surgeon's discretion to either place a stent and do a staged second look at a later time, proceed with ureteroscopy without a sheath, or balloon dilate.

Pre-operative data collection will include age, race, gender, ASA (American Society of Anesthesiologists) score (for comorbidity assessment), body mass index (BMI), and disease history, including stone disease, prior ureteroscopic procedures, vascular disease, and pelvic radiation. Disease fields that will be obtained include stone size (maximal axial and coronal dimensions), degree of hydronephrosis (mild/moderate/severe), and duration of prior ureteral stenting (if applicable).

Intra-operative data will include recording any buckling, kinking, or difficulty in instrument passage that occurs. Surgeons will be asked to subjectively rate the ease of sheath placement, stone extraction through sheath (if applicable), and ease of instrument passage on a scale 1 to 4, with 1 being poor and 4 being excellent. Ureteroscopic video will be taken for all procedures, and ureteral wall injuries will be evaluated after removal of the UAS by a urologist ([name]) blinded to the treatment device using the classification methodology previously described by Traxer and Thomas [3].

UAS related injuries determined by ureteroscopic video will be categorized into five (or 4 per PULS) grades, ranging from 0-4, defined by the following characteristics:

- Grade 0: No ureteral lesion or only mucosal petechiae
- Grade 1: Mucosal erosion or a mucosal flap without smooth muscle injury
- Grade 2: Damage to the mucosa and smooth muscle but no adventitia, with no retroperitoneal tissue visible
- Grade 3: Injury indicating ureteral perforation involving the full thickness of the ureteral wall, including the adventitia
- Grade 4: Total ureteral avulsion

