Location of the primary injury site(s) (lumbar, iliac, pelvic ureter) will also be noted to determine impact on development of future pathology including stenosis, fistula or ureteral stone formation.

Perioperative fields will include OR (surgical) time, type of anesthesia, laser fiber size, guidewire specifications, need for dual lumen catheter or introducer catheter, settings of lithotripsy (if applicable - rate/energy), use of active extraction for fragments (include basket/grasper specifications), any device breakage or damage, and intraoperative complications.

All other procedures associated with standard of care for ureteroscopic treatment of stones, including stent placement, will be left to the discretion of the investigator. Postoperative fields will include postoperative complications, need for ancillary procedures, development or persistence of hydronephrosis/obstruction, and stone-free status at 4 to 6 week postoperative imaging as determined by ultrasound of kidneys, ureters and bladder.

Sample Size

A recent prospective study evaluating ureteral damage in 359 patients undergoing ureteroscopy with a 12/14F diameter sheath found that when using the same 5-point ureteral damage classification system, low grade ureteral injury (score of 0-1) occurred in 86.6% (311/359) of patients, and high grade (score of 2-4) occurred in 13.3% (48/359) of patients.

Based on this preliminary data, the study is powered to detect whether there is a difference between device designs to cause low (0-1) vs. high grade (2-4) ureteral injury. Using an alpha of 0.05 and beta of 0.80, and assuming a difference greater than 20% between groups is considered significant, approximately 49 patients will be required per arm, for a total of approximately 98 patients.

We are requesting the IRB allow for a total enrollment of 117 patients to account for screen failures (inability to gain access, rigid ureteroscopy required, strictures, etc).

Recruitment and Consent

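### Randomised patients in whom no sheath is ever placed are excluded from the powered injury comparison, and no grading rule covers them

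*Combined protocol and SAP*

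**What the plan says.** All references are to the Combined protocol and SAP.

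- **Powered endpoint (Sample Size).** "the study is powered to detect whether there is a difference between device designs to cause low (0-1) vs. high grade (2-4) ureteral injury". The target is about 49 per arm, 98 in total.
- **How injury is graded (Research method).** "Ureteroscopic video will be taken for all procedures", and "ureteral wall injuries will be evaluated after removal of the UAS by a urologist" who is blinded to the device. The object of grading is limited to sheath-related injury: "UAS related injuries determined by ureteroscopic video will be categorized into five (or 4 per PULS) grades".
- **When no sheath can be placed (Research method, backup sheaths).** "If access has not been obtained after randomization to 6 sheaths, the patient will be considered a failure". The surgeon may then place a stent and stage the procedure, or "proceed with ureteroscopy without a sheath, or balloon dilate". No injury-grading rule is attached to any of these routes.
- **Exclusion (Research method, sheath size).** "patients will be excluded from the study if unable to gain ureteral access, or if ureteral balloon dilation or semi-rigid ureteroscopy is required" for access.
- **Enrolment allowance (Sample Size).** Enrolment of 117 is requested to cover screen failures. Inability to gain access is listed first, followed by rigid ureteroscopy, strictures and other reasons.
- **Planned recruitment (Recruitment and Consent).** 100 randomised subjects.
- **Analysis (Data Analysis Plan).** Ureteral damage is compared between groups. No analysis population and no rule for a missing grade are given.

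**The concern.** Access failure is not a screening event here. Under the backup-sheath paragraph it becomes known only after the patient has been randomised and assigned sheaths have been advanced and have failed. Excluding such patients conditions the safety outcome on a post-randomisation event that the device can influence. The protocol itself treats access as something that may differ between devices, since obtaining and maintaining access is part of the primary objective.

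A failed insertion is also exposure to the randomised device and could cause the injury being graded. Two things are at stake:

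- The reported high-grade rate may be lower than the rate among all patients in whom a sheath was tried.
- If one device leads to more final failures, or to more injury among failures, those cases leave its own numerator and denominator. The hypothesis is similar safety, so a distortion that hides a difference would favour the expected conclusion.

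This is separate from how access is counted. Counting these patients as access failures would still leave their injury grade undefined.

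**Working it through.** **1. The plan's own figures.** The reference high-grade rate is p = 48/359 = 13.37%. The 49 per arm is recovered within one patient as an equivalence calculation: n = 2p(1 − p)(z0.95 + z0.90)²/0.20² = 2 × 0.1337 × 0.8663 × (1.645 + 1.282)²/0.04 = 49.6. Read as a two-sided difference test, 13.4% versus 33.4%, it would need 70 per arm. That is a separate matter; the present point holds on either reading.

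**2. How many patients could be omitted.** The documents give no access-failure rate, only two indirect figures:

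- Enrolment allowance: 117 − 98 = 19, and 19/117 = 16.2%. This is an upper figure because the 19 also cover other reasons. Stricture, for one, is an eligibility exclusion.
- Planned randomisation: 100 − 98 = 2, and 2/100 = 2%.

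**3. Effect on one arm's high-grade rate.** Let f be the share omitted and q the high-grade rate among them. The plan reports p; the rate in all patients with an attempted sheath is (1 − f)p + fq, so the shift is f(q − p). The values of q are assumptions, since the documents give none.

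| f | q = 27% | q = 50% | q = 100% (maximum) |
|---|---|---|---|
| 2% | 0.3 points | 0.7 points | 1.7 points |
| 16.2% | 2.2 points | 5.9 points | 14.0 points |

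At q = p the shift is zero; below p it reverses.

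**4. Effect on the difference between devices.** Assume 49 graded per arm at 13.37% (6.55 expected high-grade cases each) and add the omitted patients by first assigned device, with the same q in both arms.

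*Upper case, all 19 randomised and ungraded:*

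- Split 9/10: 0.5 points at q = 50%, 1.2 points at q = 100%.
- Split 5/14: at q = 50%, (6.55 + 7)/63 − (6.55 + 2.5)/54 = 21.5% − 16.8% = 4.7 points; at q = 100%, 32.6% − 21.4% = 11.2 points.
- Split 0/19: 10.2 points at q = 50%, 24.2 points at q = 100%.

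*Lower case, 2 ungraded:*

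- Split 1/1: no difference for any common q.
- Split 0/2: at most (6.55 + 2)/51 − 6.55/49 = 16.8% − 13.4% = 3.4 points.

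For scale, the standard error of the difference at 49 per arm is √(2 × 0.134 × 0.866/49) = 6.9 points, and Sample Size treats 20 points as the difference of interest.

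**5. How wide reported bounds would be.** With one ungraded patient per arm, one scored high and the other low, the difference moves by 1/50 = 2.0 points. With 9 and 10 ungraded, the opposite extremes give (6.55 + 10)/59 − 6.55/58 = 28.1% − 11.3% = 16.8 points. Bounds are tight near 2% and wide near 16%, which is why grading the available video matters.

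**The case against.** The strongest reply has four parts.

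**Not every failure lacks a view.** A reader might infer from the grading sentence that never-placed patients cannot have an injury score. The documents do not support that: the sentence fixes when grading is done, and video is taken for all procedures. A patient who goes on to ureteroscopy without a sheath could be graded, and access may follow balloon dilation. Only the patient who is stented and staged clearly has no view at that procedure. This stands, but no rule says that the available video will be graded, and the exclusion rule removes these patients anyway.

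**Not every heavily instrumented ureter leaves.** A reader might infer that the most instrumented ureters drop out as a class. Patients rescued by a later sheath, after as many as five failed attempts, stay in and are graded. Only those in whom the whole sequence fails are affected. This stands.

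**The backup sequence dilutes device dependence.** Failure of the first sheath removes nobody. The backups are not named, but only two devices are listed, so the sequence probably includes the other one. Final failure may then depend mostly on the ureter, which randomisation balances in expectation. This weakens the case for a large between-arm bias. It does not exclude one, because the first device tried may affect what follows, and it does not address the understated rate.

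**The remedy changes what is measured.** The 48/359 benchmark comes from patients treated with a sheath. Analysis by first assigned device also credits that device with injury from backups. Both costs are real and should be stated. Scoring stent-only patients from recorded complications would replace blinded video grading with operator reports and would not detect grade 2, so it cannot carry the primary analysis.

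**Conclusion.** The point holds in a limited form. By stated rule, the plan removes randomised patients in whom access is never gained, while elsewhere calling the same patients failures. No grading rule covers them. The powered comparison therefore omits patients exposed to failed attempts.

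The high-grade rate is understated if injury among these patients exceeds 13.4%. The device comparison is biased if final failure (given such excess injury), or injury among failures, differs by first assigned device. A reader might go further and infer that the result is necessarily pushed towards similarity. The documents give neither a failure rate nor an injury rate by device, so neither direction nor size can be derived.

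The plausible range is wide. At about 2% omitted, one arm's rate moves by at most 1.7 points. At the 16.2% upper figure it moves by at most 14.0 points, and the hidden difference runs from about 0 to 1 point under a balanced split to 4.7 to 11.2 points under a 5/14 split with 50 to 100% high-grade injury. The 24.2 points of the one-arm extreme is a mathematical limit, not an expectation. All of this assumes 13.4% among graded patients in both arms. The change is worth making because it is cheap and the loss is avoidable.

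**What to change.** 1. Reconcile the two Research method paragraphs and Sample Size on whether these patients are exclusions, failures or screen failures, so that they stay in the study for analysis. Clinical handling after failed access need not change.
2. In the Data Analysis Plan, define the injury analysis set as all patients in whom a randomised sheath was advanced, analysed by first assigned device.
3. Have the same blinded reader grade the existing video whenever ureteroscopy goes ahead without a sheath.
4. Treat patients with no ureteroscopic view, such as stent only, as missing. Report bounds with all of them low grade and all of them high grade. Use recorded perforation or avulsion only in a sensitivity analysis.
5. Report placement failure by arm beside the injury result, and keep the placed-sheath comparison as a supportive analysis for consistency with the 48/359 benchmark.

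The cost is protocol wording and a few more existing videos for the same reader. The downsides are a possibly slightly higher reported injury rate, some ungraded patients handled by bounds, and injury from backup sheaths counted under the first assigned device.

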Based on current volumes of ureteroscopic procedures, we anticipate approximately 2-3 patients per week will be randomized requiring a total of approximately 9-12 months of active enrollment between to reach a total of 100 randomized subjects. Patients will be recruited from either office visits or inpatient hospitalizations. The study coordinator will consent patients using the uploaded consent form accompanying this document. All procedures, devices and protocols are standard of care. There is no additional cost to the patient outside of standard care. The patient's insurance company will be billed for medical costs.

Data Analysis Plan

Data analysis will involve comparisons of ureteral damage between groups related to device design, gender, age, BMI, preoperative stenting, prior stone disease, and prior stone procedures. Differences in operative time, ease of placement, ability to maintain access, and ease of instrument passage will also be evaluated between devices, as well as post-operative complications, success rates, and device failure rates. The analysis will be completed by the approved researchers in coordination with a CCF biostatistician [name]. Study data will be stored on the RedCap database. Data may also be stored on encrypted CCF issued IronKey and encrypted CCF issued computers. Signed consent forms will be stored in a compartment with a lock for the duration of the trial. Approved researchers on this IRB will have access to these data.

Adverse Events and Data Monitoring Committee

The investigator will report any adverse events to the IRB within 10 days of awareness. A data monitoring committee will not be used. The primary risk to participants will be the loss of confidentiality, which will

be maintained by physical and electronic locks. Any unexpected findings of concern will be communicated face-to-face to the patient by the investigator in a clinic visit. A Data Monitoring Committee will not be used for this study as the devices and procedures used are standard care.

Study Costs

REFERENCES

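### The stated 49 per arm does not give 80% power for 13.3% vs 33.3% high-grade injury (about 65% two-sided, 76% one-sided); arm rates, sidedness and test are unstated, and nothing stops a non-significant result being read as similar safety

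*Combined protocol and SAP*

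**What the plan says.** All of the following is in the combined protocol and SAP.

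- **Sample Size, reference rate.** In an earlier cohort, "high grade (score of 2-4) occurred in 13.3% (48/359) of patients".
- **Sample Size, aim.** On the basis of that rate, "the study is powered to detect whether there is a difference between device designs to cause low (0-1) vs. high grade (2-4) ureteral injury".
- **Sample Size, error rates.** "Using an alpha of 0.05 and beta of 0.80". A beta of 0.80 would mean 20% power, so this is evidently a slip for power of 0.80.
- **Sample Size, result.** "assuming a difference greater than 20% between groups is considered significant, approximately 49 patients will be required per arm", or about 98 in total.
- **Sample Size, allowance.** "We are requesting the IRB allow for a total enrollment of 117 patients to account for screen failures".
- **Hypothesis.** "We hypothesize that the modified designs of Re-Trace and Parallel devices will demonstrate similar safety profiles".
- **Data Analysis Plan.** "Data analysis will involve comparisons of ureteral damage between groups related to device design", followed by a list of patient factors.

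The document does not give the two assumed arm rates, the number of sides, the test, an equivalence or non-inferiority margin, a confidence-interval criterion, or a rule for interpreting a non-significant result.

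**The concern.** There are two linked problems.

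First, this is the study's only power statement, and it supports one of its primary objectives, ureteral injury. A reader who puts the printed rate and the printed difference into a standard two-proportion calculation does not get 49. The power claim therefore cannot be checked, and on the usual reading it is too high.

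Second, the calculation is worded for detecting a difference while the hypothesis is similarity. Those two designs draw opposite conclusions from a null result. With no test or decision rule in the Data Analysis Plan, a non-significant p-value could be presented as confirming the hypothesis even though the data still allow the 20-point difference that the protocol treats as important. High-grade injury here includes perforation and avulsion.

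**Working it through.** **Inputs.** From Sample Size: rate 0.133, difference 0.20, alpha 0.05, power 0.80, 49 per arm. Assumed, because not stated: the 20% is in percentage points, allocation is 1:1, and sidedness and test are as labelled below. A relative 20% change from 13.3% would need more than 2,300 per arm, so it cannot be what was meant. A 20-point fall from 13.3% is impossible, so the only contrast with 13.3% in one arm is 0.133 vs 0.333.

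**Trying to reproduce 49 (pooled normal approximation).** With p̄ = (0.133 + 0.333)/2 = 0.233:

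n per arm = [z_α √(2p̄(1−p̄)) + z_β √(p₁(1−p₁) + p₂(1−p₂))]² / (p₂−p₁)²

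The two square roots are 0.5978 and 0.5809, and z_β = 0.8416.

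- Two-sided: (1.960 × 0.5978 + 0.8416 × 0.5809)² / 0.04 = 1.6606² / 0.04 = 68.9, so **69 per arm**. Unpooled variance gives 66.2, arcsine 67.1 and continuity correction 78.6. Fisher's exact test first reaches 80% at 77.
- One-sided: (1.645 × 0.5978 + 0.8416 × 0.5809)² / 0.04 = 1.4723² / 0.04 = 54.2, so **55 per arm**.

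Neither gives 49.

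**Power at 49 per arm for 0.133 vs 0.333.**

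- Two-sided: z = (0.20 × √49 − 1.960 × 0.5978) / 0.5809 = (1.400 − 1.172) / 0.5809 = 0.393, so power is **65.3%**.
- One-sided: z = (1.400 − 0.983) / 0.5809 = 0.717, so power is **76.3%**.

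**Other readings at 49 per arm.** Exact figures come from enumerating all outcomes.

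| Rates | Sides | Pooled n for 80% | Power: normal / exact chi-square / Fisher |
|---|---|---|---|
| 13.3% vs 33.3% | 2 | 68.9 | 65 / 66 / 58% |
| 13.3% vs 33.3% | 1 | 54.2 | 76 / 77 / 70% |
| 10% vs 30% | 2 | 61.6 | 70 / 73 / 63% |
| 5% vs 25% | 2 | 48.8 | 80 / 85 / 74% |
| 3.3% vs 23.3% (centred on 13.3%) | 2 | 44.1 | 84 / 90 / 79% |

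Two further calculations land near 49:

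- 10% vs 30% one-sided: 48.4.
- Equivalence by two one-sided tests, 13.3% in both arms, margin ±20 points: (1.645 + 1.282)² × 2 × 0.133 × 0.867 / 0.04 = 49.4.

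**What 49 per arm delivers.** With 13.3% in one arm and a two-sided test, 80% power is reached at a difference of about 24 points (about 26 with Fisher).

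**Does the enrolment allowance close the gap?** If all 117 were analysed (58 per arm), power for 13.3% vs 33.3% would be 73% (74% exact chi-square, 67% Fisher). The allowance is in any case reserved for screen failures.

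**Risk of misreading a null result.** At a true 13.3% vs 33.3%, the chance of a non-significant two-sided result is 1 − 0.664 = 34% (chi-square) or 1 − 0.577 = 42% (Fisher). As a made-up illustration, 7/49 vs 13/49 is a difference of 12.2 points with p = 0.13 (chi-square) or 0.21 (Fisher). Its Wald 95% interval runs from −3.5 to +28.0 points, so 20 points is not excluded.

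**The case against.** The strongest reply is that no arithmetic error is proved. The shortfall appears only once the reader supplies 13.3% vs 33.3% for a difference test, and the protocol does not commit to either. One calculation uses the printed rate, difference, alpha and power and lands on the stated figure: equivalence within ±20 points with 13.3% in both arms gives 49.4. It also fits the hypothesis of similar safety. If that was the design, quoting 65% power for a difference test describes a trial the sponsor did not plan. Nor does the plan anywhere say that a non-significant result will be taken as similarity.

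Much of this stands. It cannot be said that 49 is simply wrong, and the shortfall has to be tied to the usual reading. But the equivalence reading contradicts the section's own statement that the study is powered to detect a difference, and no margin or equivalence test is declared. The 5% vs 25% and 10% vs 30% readings use rates found nowhere in the document. Centring on 13.3% gives 44, or 54 with continuity correction, not 49. That several incompatible designs fit roughly equally well confirms that the plan does not say which one it is. The misreading is a risk rather than a stated intention, but nothing in the plan guards against it.

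**Conclusion.** The concern holds and should be fixed. On the usual reading (percentage points, 13.3% in one arm, a test for a difference), 49 per arm gives about 65% power two-sided and 76% one-sided, against the claimed 80%. Choosing one side or the other does not rescue the figure; 80% needs about 69 or 55 per arm.

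The size of the shortfall depends on that reading. Across the two-sided readings above, power at 49 runs from 58% to 90% according to rates and test. Three things do not depend on it: the arm rates, sidedness and test are missing; the hypothesis of similarity does not match a calculation for a difference; and no rule prevents a non-significant result from being reported as similar safety.

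**What to change.** Keep the sample size and state what it delivers. The sponsor should first establish which calculation produced 49, then align three sections.

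- **Sample Size.** Replace the beta of 0.80 with power. State the arm rates, sidedness, test and the power they give, for example: *Two-sided alpha 0.05, chi-square test; 49 per arm gives about 65% power for 13.3% vs 33.3% (58% with Fisher's exact test) and 80% power for a difference of about 24 points.* If other rates or a one-sided test were used, state and justify those, with their power.
- **Data Analysis Plan.** Name that test for high-grade (2–4) against low-grade (0–1) injury, report the difference with its 95% confidence interval, and add: *A non-significant result will not be read as showing similarity.*
- **Hypothesis.** Align it, for example: *The study tests for a difference in high-grade injury and is not designed to demonstrate equivalence.*

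If the sponsor confirms that equivalence was the original design, the plan should instead declare two one-sided tests with a justified margin and a 90% confidence-interval rule, before injury is compared by arm.

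**Cost.** Wording only, and no extra patients. The drawback is a less favourable power figure: about 65% in place of 80% on the 13.3% vs 33.3% reading.

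Holding 80% two-sided on that reading would need 2 × 69 = 138 analysed patients, or 138 × 117/98 ≈ 165 enrolled. Recruitment and Consent says "we anticipate approximately 2-3 patients per week will be randomized" and allows about 9–12 months for 100. At that rate 138 patients take 46–69 weeks, against 33–49 weeks for 98. If the screen failures arise after randomization, up to 165 would have to be randomized, taking about 55–83 weeks. That is why restating the power is proposed rather than enlarging the trial.

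### Some of the screen failures that justify enrolling 117 arise after randomisation, while the forecast of 100 randomised leaves room for only two such losses against the 98 required

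*Combined protocol and SAP*

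**What the plan says.** All references are to the combined protocol and SAP.

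- **Sample Size** sets the requirement: "approximately 49 patients will be required per arm, for a total of approximately 98 patients". It then asks the IRB for a "total enrollment of 117 patients to account for screen failures (inability to gain access, rigid ureteroscopy required, strictures, etc" (the bracketed list closes there).
- **Research method** lists ureteral stricture among the ordinary eligibility exclusions. It also excludes patients in whom ureteral access cannot be gained, or in whom balloon dilation or semi-rigid ureteroscopy is needed to gain it.
- **Research method**, further on, sets out a sequence of backup sheaths that begins "If unable to obtain access with the initial sheath the patient is randomized to". A patient still without access after six sheaths is classed as a failure; that paragraph does not call the patient excluded.
- **Recruitment and Consent** expects that "approximately 2-3 patients per week will be randomized", over "approximately 9-12 months of active enrollment", "to reach a total of 100 randomized subjects".
- **Purpose and Objectives** makes obtaining and maintaining access part of the primary objective, alongside ureteral injury.

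No section says when randomisation takes place, how the 19 extra patients divide between losses before and after it, or whether an excluded randomised patient is replaced.

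**The concern.** A screen failure is normally a patient who leaves before allocation. Failed access with a randomised sheath cannot be that, because the patient already has an assignment when it happens. The need for rigid ureteroscopy is also found in the operating room, although the documents do not say whether before or after allocation.

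Two things are at stake. The first is the count: a team working to 100 randomised has almost no margin for losses that the plan itself expects and partly places after randomisation. The second is who is counted. The same patient is excluded by one paragraph of Research method, classed as a failure by a later one, and called a screen failure under Sample Size. Since obtaining access is part of the primary objective, removing access failures removes outcomes from the comparison the trial was set up to make.

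**Working it through.** **Inputs.** Required 98 (49 per arm) and enrolment 117, both from Sample Size. Randomised 100 and accrual of 2 to 3 per week, both from Recruitment and Consent.

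**The plan's own figures.** 2 × 49 = 98. With p = 48/359 = 0.1337, the reference rate of high-grade injury, 49 per arm is nearly reproduced by an equivalence calculation with a 20-point margin:

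2p(1−p)(z₀.₉₅ + z₀.₉₀)² / 0.20² = 49.6 per arm.

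A two-sided test to detect 13.4% against 33.4% would need about 70 per arm. That is a separate question. Here 98 is taken as the plan's target, and because its basis is unclear no power figure is attached to a shortfall.

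**Allowance.** 117 − 98 = 19, and 19/117 = 16.2% of those enrolled.

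**Do the three counts fit?**
- Losses before randomisation: 117 − 100 = 17.
- Losses after randomisation: 100 − 98 = 2.
- Total: 17 + 2 = 19, which equals the allowance.

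So they fit only if 2/19 = 10.5% of the allowance falls after randomisation.

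**Evaluable patients if recruitment ended at 100 randomised.** Let f be the share of the 19 that falls after randomisation. Of 117 enrolled, 98 + 19f are randomised and 98 are evaluable, so the evaluable number per 100 randomised is 100 × 98/(98 + 19f).

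| f | Evaluable of 100 |
|---|---|
| 0 | 100 |
| 10% | 98.1 |
| 25% | 95.4 |
| 50% | 91.2 |
| 75% | 87.3 |
| 100% | 83.8 |

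A cruder version applies half of the 16.2% directly to the 100: 100 × (1 − 0.081) = 91.9. Hence about 91 to 92 for the half-and-half case. The last row is about 84, or 42 per arm, which is 14 short.

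**Accrual** (52.18/12 = 4.35 weeks per month).
- 100 randomised: 100/3 to 100/2 = 33.3 to 50 weeks, or 7.7 to 11.5 months.
- 117 randomised: 117/3 to 117/2 = 39 to 58.5 weeks, or 9.0 to 13.5 months.

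Both ranges overlap the stated 9 to 12 months, so the timeline does not show which total is meant.

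**The case against.** A reader might infer that the trial will close with 84 evaluable patients and lose power accordingly. The documents do not support that.

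- **No stopping rule.** The 100 appears in an accrual forecast. The only stated limit is the requested enrolment of 117. This stands; what remains is that 100 is the only randomised total the documents give.
- **The 16% is a loss from those enrolled.** Taken over 117 enrolled, 117 − 19 = 98 whatever the split. To enrol 117, randomise 100 and end with 84 would take 17 losses before and 16 after, 33 in all, against 19 allowed. The figure of 84 therefore requires that every allowed loss falls after randomisation and that recruitment stops at 100, with the 117 never used. This stands, and it makes 84 the extreme case.
- **Not every listed reason comes after randomisation.** Stricture is an eligibility exclusion and can be found earlier, the list is open-ended, and the timing of rigid ureteroscopy relative to allocation is not stated. This stands.
- **Complete access failure may be uncommon.** Up to six sheaths may be tried, and no failure rate is given. This is fair, and it is why only a range can be stated.
- **Keeping everyone does not by itself give 98 injury grades.** Injury is graded after the sheath is removed, so a patient in whom no sheath was placed has no sheath-related grade. This stands, and the fix has to allow for it.

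None of this removes the core: the first listed screen failure comes after randomisation, its status differs between paragraphs, and 100 randomised tolerates two such losses.

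**Conclusion.** The point holds as an inconsistency in counting, with a conditional effect on numbers; it is not a demonstrated shortfall. At least one listed screen failure, failed sheath access, arises after randomisation, and the need for rigid ureteroscopy possibly does. The documents disagree on whether such a patient is excluded or counted as a failure.

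If recruitment ended at 100, evaluable numbers would run from about 98, with a tenth of the allowance falling after randomisation, through 91 to 92 at half, to about 84 at worst. The range assumes that the plan's 16.2% allowance is right and that excluded patients are not replaced. The split that would settle it is not given. The matter should be corrected, because the present wording leaves both the evaluable number and the analysed population undetermined.

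**What to change.** Reconcile Research method, Sample Size, and Recruitment and Consent under one counting rule:

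1. State when randomisation takes place, and reserve the term screen failure for exclusions made before it.
2. Keep every randomised patient in the analysis by assigned sheath. Count failed access as a failure on the access objective, and remove the conflict between the two paragraphs of Research method on such patients.
3. In Recruitment and Consent, replace the 100 with up to 117 randomised, until 98 have an injury grade. On the plan's own allowance, 117 enrolled yields 98 however the 19 losses divide.
4. Report by assigned sheath how many randomised patients have no injury grade and why, since the graded patients are a subset of those randomised.

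The cost is wording in three sections and no enrolment beyond the 117 already requested. Accrual could take about 9 to 13.5 months at most, against about 8 to 11.5 months for 100, so the upper end would exceed the stated 12 months by about 1.5.
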